Specific Aims:

There are 3 specific aims for this study during the grant period:

- D. Develop a feasible protocol for obtaining QbMRI for children presenting to the emergency department with acute head injury.
- E. Prospectively test the diagnostic accuracy of qbMRI for detection of acute pediatric TBI in the emergency care setting compared to head CT as the reference standard.
- F. Evaluate the feasibility of obtaining QbMRI in the emergency department to assess acute pediatric brain injury, including need for sedative medications, time to imaging, and provider satisfaction.

Outcomes:

1. Primary Outcome: Test characteristics of QbMRI to detect acute pediatric TBIs, including sensitivity, specificity, positive/negative predictive value and positive/negative likelihood ratios.
2. Secondary Outcomes: Develop formal protocol to be employed for further clinical evaluation and trials on QbMRI in pediatric head trauma; assess feasibility of obtaining QbMRI in the emergency department to include need for anxiolysis/sedation, time to imaging and provider satisfaction.

Hypothesis:

We hypothesize there is no significant difference of sensitivity and specificity of QbMRI for detection of clinically important traumatic brain injuries as compared to non-contrast head CT in patients less than 15 years presenting with head trauma. We hypothesize that it will be feasible to obtain QbMRI in the emergency department without increased use of anxiolysis/sedation or prolonged time to obtain imaging

4. Study Design:

Overview: The study will be a prospective cohort study of diagnostic accuracy comparing QbMRI (index test) to non-contrast head CT (reference test). Children being evaluated for acute TBI with head CT will then undergo QbMRI in the emergency department. Only subjects who the attending physician has decided to obtain neuroimaging in will be enrolled; therefore subjects will not undergo imaging just for the study. The results of the QbMRI will not be used for clinical care. All images will be de-identified prior to review by the neuroradiologist including patient name, hospital and date.

5. Study Population:

Inclusion criteria:

1. The patient presents to the pediatric emergency department or trauma system at OHSU or is a trauma system transfer patient to OHSU
2. Age 0-14 years.
3. Being evaluated for a traumatic head injury and attending physician decides to obtain a head CT.

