4. Clinically stable for additional testing: provider deems it safe to obtain a QbMRI in the ED without deep sedation

Exclusion criteria:

1. Subject is from outside hospital and head CT was performed greater than 6 hours prior
2. Subject is from outside hospital and initial head CT is not in our imaging system for review
3. History of intracranial surgery
4. History of metallic implants making MRI contraindicated
5. Decompressive surgery prior to QbMRI

Study Procedure:

The Clinical Research Investigative Study Program (CRISP) volunteers who are on duty in the emergency department between the hours of 7 am and 11 pm will screen all ED patients for eligibility including pediatric trauma system entries. They will identify possible subjects based on suggestive chief complaints (e.g. head injury, trauma, fall, etc.) and approach the attending physician about whether the subject is being evaluated for possible acute head injury and will be receiving neuroimaging. If so, they will approach the family and review the consent forms with them for participation. After subjects are found to be eligible (see above inclusion/exclusion criteria) and consented, the physician will order the study QbMRI to be done after the head CT. QbMRIs are available to our pediatric ED at all hours as it is standard of care for other indications as described previously. Subjects will only be enrolled in the study if the attending physician feels they warrant neuroimaging with a head CT. After undergoing a QbMRI, their clinical care will be the same whether they are in the study or not. A copy of the images will then be de-identified and placed in separate review folders in the electronic radiology system so they cannot be linked (ie. One folder for head CTs and one folder for QbMRIs) for review by an attending neuroradiologist. Clinical data including length of stay, procedures performed and disposition will be collected directly from EPIC.

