QbMRIs will be obtained in the MRI scanner at OHSU available to the ED. The protocol will consist of a QbMRI protocol modified to include a blood-sensitive T2* sequence. No intravenous contrast will be administered. It is not anticipated that any sedation or anti-anxiety drugs will be administered to patients. However, this is reflected in the consent that a small portion of children will need for any type of neuroimaging. For this reason, parents may decline participation. No deep sedation drugs will be administered as that will fall under the definition of clinically unstable in the exclusion criteria. The protocol consists of:

- Coronal single-shot T2 weighted ultrafast spin echo
- Sagittal single-shot T2 weighted ultrafast spin echo
- Axial T2* weighted gradient recall echo

After a subject undergoes their imaging in the MRI suite, their further disposition will be selected by the attending physician as what they feel is necessary including admission to the hospital, observation or discharge.

Traumatic Brain Injury on neuroimaging will be defined as previously published¹ to include:

- Intracranial hemorrhage or contusion
- Cerebral edema
- Traumatic infarction
- Diffuse axonal injury
- Shearing injury
- Midline shift of intracranial contents or signs of brain herniation
- Skull fracture depressed by at least the width of the table of the skull
- Pneumocephalus

Number of Subjects:

A total of 100 subjects will be enrolled in this pilot study. To generate an approximate study timeframe and potential patient sample, EPIC was accessed to identify all patients less than 19 years of age who were seen in the OHSU emergency department in 2015 and had a “CT Head WO contrast (CPT code 70450)” performed while in the ED. This resulted 363 patients. As a large referral center, OHSU receives many transfers from outside hospitals. In our retrospective data of trauma system activations, the majority were transfer patients with head injuries. These numbers would not be included in the 363 most likely as their neuroimaging was done at an outside hospital. A review of the trauma registry at OHSU for the year of 2015 and patient less than 19 years of age resulted 221 patients who had head and neck injuries. There is most likely overlap between these 2 data points as some trauma registry patients were not transfers and underwent head CT in our department. However, we would conservatively expect that 400 patients may be eligible for this study during a 12 month period.

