
To assess the adequacy of this proposed pilot sample, we calculated the number of positive head CTs obtained in our department. Our rate of positive findings were better than the previous study mentioned rate of 2.5% positive head CTs of all ordered. At OHSU 10% of CTs in patients less than 19 years of age were positive for an acute intracranial injury. This was generated by applying the above search criteria in EPIC and associated an intracranial injury final diagnosis code including epidural hematoma, subdural hematoma, subarachnoid hemorrhage, intracranial bleed, skull fracture and cerebral contusion. This is a very conservative estimate as the majority of transfer patients through the trauma system will have positive neuroimaging as the reason for transfer and further pediatric subspecialty care. With these numbers we would expect to enroll the 100 patients within 1 year and have at least 10-20% with a positive acute TBI when taking into account the positive imaging rate in the OHSU emergency department and transfer patients with positive imaging.

Vulnerable Populations

This study, by design, is focused on pediatric patients. It may include other vulnerable populations such as pregnant women and minorities, though they are not the focus of the study

and are not included in screening criteria. No pregnant women will be given an MRI knowingly. Prisoners will not be included in this study.

Setting

The Doernbecher Children's Hospital emergency department

Consent Process

All parents will be consented on presentation to the emergency department by a member of the study team including the CRISP team. Please find attached consent form. All children ages 7-14 will be asked to signed the assent form as well.

We are requesting a consent/HIPAA waiver for a select group of patients. Any patient who is excluded from the study after initial screening for any reason other than the LAR refusing to be included will be reviewed by the principal investigator. If the clinical team, without any input from the research team, has obtained the same imaging test this study is evaluating, QuickBrain MRI, the study team will use the imaging and data as in the rest of the protocol under a waiver. It is not possible to obtain consent due to the short time window of being in the ED. Due to the acute nature of the injuries they do not have follow up in the ED either to allow consent.

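### The masked CT and QbMRI reads have no set reading order, shuffling, locking or washout, so if one neuroradiologist reads both, recall can bias the primary accuracy estimates.

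*Combined protocol and SAP*

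**What the plan says.** Each child has a head CT, the reference test, followed by a QbMRI, the index test (4. Study Design, Overview). The Overview gives the first masking step: "All images will be de-identified prior to review by the neuroradiologist including patient name, hospital and date". Study Procedure, under 5. Study Population, gives the second: the copies of the two kinds of scan are filed apart, "so they cannot be linked (ie. One folder for head CTs and one folder for QbMRIs) for review by an attending neuroradiologist".

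The reads feed the primary outcome (Outcomes): "Test characteristics of QbMRI to detect acute pediatric TBIs, including sensitivity, specificity, positive/negative predictive value and positive/negative likelihood ratios".

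For these reads the combined protocol and SAP does not say:

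- whether the same person or different people read the two folders;
- which folder is read first;
- whether cases are shuffled within a folder;
- whether one set of reads is locked before the other is opened;
- whether an interval separates the two sessions;
- whether the research reader may have reported a child's clinical CT.

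Data Analysis describes the raters of enlarged perivascular spaces as blinded. It has no equivalent sentence for the primary reads. The two independent fellows in Preliminary Data belong to the earlier retrospective study, not to this one.

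**The concern.** In a paired accuracy study the index test should be read without knowledge of the reference result, and the reference without knowledge of the index. Removing labels and separating folders stops a reader from matching scans by name or date. It does not stop a reader from recognising a child from the images, or from case position if both folders happen to fill in enrolment order. The plan, followed exactly, would allow one person to read the whole CT folder and then the QbMRI folder on the same day.

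Recall pulls the two reads toward agreement. If CT is read first, a lesion that would have been missed on QbMRI may be called present. If QbMRI is read first and CT soon after, the reference itself may drift toward the QbMRI call. In either case the confidence interval does not show the problem, and it cannot be removed once unprotected reads have been made. Preliminary Data says this pilot is to examine the gap between sensitivity for radiographic lesions and for clinically important ones, and to guide a multicenter study. Recall could blur that comparison.

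**Working it through.** The plan states no figure on this point, so there is nothing to reproduce. The check is a comparison of texts followed by an illustration of scale.

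**Text.** 4. Study Design and Study Procedure both use the singular for the neuroradiologist. Neither states that one person reads both folders, and neither provides for two readers. No section supplies any of the items listed as missing above.

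**Inputs.**

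- Enrolment (Number of Subjects): "A total of 100 subjects will be enrolled in this pilot study".
- Expected positives (Number of Subjects): "have at least 10-20% with a positive acute TBI". So 100 × 0.10 = 10 to 100 × 0.20 = 20 children. The plan says at least, so 20 is not a ceiling.
- True sensitivity, for illustration: s = 85%, the retrospective estimate for any radiographic injury (Preliminary Data, 95% CI 73 to 93).
- Share of misses turned into detections by recall: r. The documents give no value. Assumed range: 10%, 25%, 50%.

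**Effect of one changed read.** With n positives, one miss recorded as a detection moves sensitivity by 100/n points.

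- n = 10: 10 points. For example, 9/10 = 90% (exact 95% CI 55.5 to 99.7) becomes 10/10 = 100% (69.2 to 100).
- n = 20: 5 points. For example, 17/20 = 85% (62.1 to 96.8) becomes 18/20 = 90% (68.3 to 98.8).

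**Expected shift if CT is read first.** Apparent sensitivity = s + r(1 − s).

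- r = 10%: 0.85 + 0.10 × 0.15 = 86.5%.
- r = 25%: 0.85 + 0.25 × 0.15 = 88.75%.
- r = 50%: 0.85 + 0.50 × 0.15 = 92.5%.

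**Chance of recording no misses at all**, which is (apparent sensitivity)^n:

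| n | no recall | r = 25% | r = 50% |
|---|---|---|---|
| 10 | 0.85^10 = 19.7% | 0.8875^10 = 30.3% | 0.925^10 = 45.9% |
| 20 | 0.85^20 = 3.9% | 0.8875^20 = 9.2% | 0.925^20 = 21.0% |

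These figures show how sensitive a small positive group is to a few changed reads. They do not estimate the bias in this trial.

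**The case against.** The strongest reply is that the study is already masked, that it is a pilot with no accuracy threshold to pass, and that what remains is a modest residual risk. Much of this stands, and it limits what can be claimed.

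- **One reader for both folders.** A reader might take this as fact. The singular wording makes it the natural reading, but it remains an inference, so the point is conditional on it.
- **An unblinded comparison.** A reader might infer this from the missing reading rules. The documents do not support it: identifiers are removed and the folders are kept apart so that scans cannot be linked.
- **Sensitivity will be inflated.** That direction needs CT to be read first, and the order is not given. With QbMRI first, recall acts on the reference read.
- **A large effect.** One could assume 15 positives and 2 misses, both rescued, so that 13/15 = 87% (exact 95% CI 60 to 98) becomes 15/15 = 100% (78 to 100). That presumes every miss is rescued, which nothing in the documents supports. A lesion hard to see on QbMRI is also a weak cue for recognising the child; distinctive lesions are likely to be detected anyway. Recall would have to work through another lesion, other anatomy or case position. Rescue is therefore possible, but probably partial.
- **The reader reported the child's clinical CT.** The plan leaves this open but does not state it. Number of Subjects indicates that transfers usually had their imaging at an outside hospital. A flat ban on such readers could also force a new reader at a single site.

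None of this supplies a reading order, shuffling, locking or washout. Pilot status lowers the stakes, but it does not make those steps costly.

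**Conclusion.** The concern holds in conditional form. The masking described is real but incomplete, and it leaves recall between the paired reads uncontrolled on the primary outcome. If one neuroradiologist reads both folders with CT first, apparent QbMRI sensitivity is likely to be pushed up. If QbMRI is read first without a washout, the CT reference may be swayed instead.

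The size is unknown because no recall rate is given. Under the assumptions shown, the upward shift in sensitivity is 1.5, 3.75 or 7.5 points for rescue rates of 10%, 25% or 50%. This rests on a single reader, CT read first and a true sensitivity of 85%. If different people were meant to read the two folders, and neither sees the other's results, most of the concern falls away. This is a cheap improvement to the plan, not a fault that invalidates the design.

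**What to change.** Add to Study Procedure:

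1. State who reads each folder, and whether it is the same person.
2. Read all QbMRIs in random order, and record and lock the results before the CT folder is opened.
3. Read the CTs in a fresh random order after a fixed washout, for example 4 weeks.
4. Where possible without adding a reader, do not assign a child's research QbMRI read to someone who reported that child's clinical CT. Where this cannot be avoided, record it and report it as a limitation.

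The cost is scheduling: reading finishes a few weeks later. The sample size is unchanged, and items 2 and 3 need no extra reader. According to 4. Study Design, QbMRI results are not used for clinical care, so later research reads do not affect the management of enrolled children. If separate readers were already intended, one sentence saying so, and confirming that each is blind to the other's results, would largely suffice.

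### Do planning counts taken from patients under 19, with no stated trauma filter, undermine the pilot's 100-patient target or its expected share of positive scans?

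*Combined protocol and SAP*

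**What the plan says.** In the combined protocol and SAP, the Number of Subjects section fixes enrolment at 100 and then gives background counts for timing and case mix.

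- **CT count.** The base is "all patients less than 19 years of age who were seen in the OHSU emergency department in 2015" with a non-contrast head CT identified by procedure code: 363 patients.
- **Registry count.** The 2015 trauma registry search, also under 19, gave "221 patients who had head and neck injuries".
- **Combining them.** Transfers are said to be mostly absent from the 363 because they were imaged elsewhere: "In our retrospective data of trauma system activations, the majority were transfer patients with head injuries". The text then concedes "There is most likely overlap between these 2 data points" and concludes "we would conservatively expect that 400 patients may be eligible for this study during a 12 month period".
- **Positive rate.** "At OHSU 10% of CTs in patients less than 19 years of age were positive for an acute intracranial injury". This comes from final diagnosis codes including "epidural hematoma, subdural hematoma, subarachnoid hemorrhage, intracranial bleed, skull fracture and cerebral contusion". The rate is called very conservative because most transfers will have positive imaging, and the section expects 10-20% or more of subjects to be positive.

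The Inclusion criteria restrict the trial to ages 0-14 and to patients "Being evaluated for a traumatic head injury and attending physician decides to obtain a head CT". The TBI definition under Study Procedure counts a skull fracture only if it is depressed. The Exclusion criteria remove transfers whose outside CT is more than 6 hours old or not available for review.

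**The concern.** The planning population differs from the trial population in three ways. It includes 15- to 18-year-olds. The 363 may include CTs done for reasons other than trauma. The 10% may count non-depressed fractures that the trial would not call TBI. The first two can only overstate the pool drawn from these sources, and the third can overstate the positive rate. The transfer exclusions are not applied either. Yet the section presents its figures as cautious or as minimums.

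Two things would be at stake: whether 100 subjects can be enrolled in a year, and how many positives there will be to estimate sensitivity. If every positive is detected, the exact 95% lower limit for sensitivity is 0.025^(1/r) for r positives: 83% with 20, 69% with 10 and 48% with 5. A real shortfall in positives would therefore widen the main interval.

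**Working it through.** **Can the stated 400 be reproduced?** Not exactly, because the overlap is not given. The union of the two counts is 363 + 221 - overlap, so it lies between 363 (full overlap) and 584 (none). The figure 400 falls inside that range and, read as a union, implies an overlap of 584 - 400 = 184.

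**Pool for ages 0-14.** Suppose most of the 221 were transfers not in the 363. The text says this of its retrospective data; applying it to 2015 is an assumption. The overlap is then at most 110 and the union is 474 to 584. The documents give no age split, so the shares below are assumed.

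| Share aged 0-14 | Pool | 100 subjects as a fraction of the pool |
|---|---|---|
| 60% | 284-350 | 29-35% |
| 15/19 (even spread) | 374-461 | 22-27% |
| 90% | 427-526 | 19-23% |

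The pool reaches 400 if the 0-14 share is at least 400/584 = 68.5% (no overlap) to 400/474 = 84.4% (half overlap). All of this is before any trauma filter or exclusion.

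**Positive rate.** 10% of 363 is about 36 coded positives. If 0, 9 or 18 of them (assumed) were isolated non-depressed fractures, the local rate becomes 36/363 = 9.9%, 27/363 = 7.4% or 18/363 = 5.0%. Two effects act the other way.

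- *Non-trauma CTs dilute the 10%.* If only 75% or 50% of the 363 were for trauma (assumed), the rate among trauma CTs is 0.10/0.75 = 13.3% or 0.10/0.50 = 20%.
- *Transfers.* At least 221 - 110 = 111 registry patients lie outside the 363, which is 111/474 = 23.4% of the pool. With 50% of them positive (assumed) and 10% locally, the overall rate is 0.234 × 0.50 + 0.766 × 0.10 = 19.4%. If half of them are excluded, their share is 55.5/418.5 = 13.3% and the rate is 0.133 × 0.50 + 0.867 × 0.10 = 15.3%. If all are excluded, it is 10%.

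**Worst fracture case combined with transfers.** With 5.0% locally, 0.234 × 0.50 + 0.766 × 0.05 = 15.5%. With half the transfers excluded, 0.133 × 0.50 + 0.867 × 0.05 = 11.0%.

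**A smaller transfer count.** If 400 is the union, only 400 - 363 = 37 patients are added. At 50% positive the overall rate is (36.3 + 18.5)/400 = 13.7%. The local rate could fall to (40 - 18.5)/363 = 5.9% before the overall share dropped below 10%.

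**The case for a change.** The strongest case for acting is that words such as *conservatively*, *very conservative* and *at least* claim minimums that no calculation for ages 0-14 supports, in a section meant to judge whether the sample is adequate. Stacked pessimistic assumptions also make the pool look thin. Take 400 as the union, half of the 363 done for trauma and 60% aged 0-14: (363 × 0.5 + 37) × 0.60 = 131. Screening only from 7 am to 11 pm, with even arrivals assumed, leaves 131 × 16/24 = 87 a year, which is below 100 before consent and stability are considered. And even at a true 10% rate, the chance of at least 10 positives among 100 is only 0.55.

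Part of this stands: neither 400 nor 10% is a demonstrated minimum for the trial's own population. The rest carries less weight.

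- *Conservatively* directly follows the admission of overlap and can be read as the discount from 584 to 400.
- *Very conservative* has a stated reason, the transfers, though it is not quantified.
- The under-19 basis is printed beside the counts and the rate, so a reader can see the limitation.
- The fracture effect may be zero, and the diagnosis list is introduced as *including* its items, so it may not be complete.
- The Consent Process section lets screened-out patients who had the same MRI clinically be added, which softens the exclusions and the screening window.
- If the pessimistic pool were true, enrolment would take longer than a year. That is a timing matter and biases no estimate.

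**Conclusion.** The mismatch is genuine, but no change to the plan follows. Age and indication can only overstate the pool from these sources. For the positive rate the net direction is unknown, because unqualified fractures may raise the 10% while non-trauma CTs in the denominator and omitted positive transfers lower it relative to the trial. On the middle assumptions (even age spread, at most half overlap) the 0-14 pool is 374 to 461 before further filters. With half of transfers positive and no more than half excluded, the positive share stays between 11.0% and 19.4%. It drops below 10% only if nearly all transfers are lost, or very few are added, and fractures are also heavily overcounted. The age shares, 2015 overlap, fracture counts and transfer positivity are assumptions throughout.

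This is a pilot with a fixed N of 100 and no power or precision target built on these counts. Eligibility, the reference standard and the analysis do not use them. The Data Analysis section reports the accuracy measures with 95% confidence intervals, so any shortage of positives will show in the results. Repeating the searches or softening three qualifiers would tidy the background text without altering any result or conclusion.

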Our initial retrospective study suggests that QbMRI has adequate sensitivity to detect acute ciTBIs in children. The study was presented at 2 national conferences in the spring of 2016 (Society for Academic Emergency Medicine and Pediatric Academic Society) with a manuscript currently under review.¹² This preliminary study included all pediatric trauma patients presenting to OHSU from 2/2010 through 12/2013 who had both a head CT and QbMRI. The current standard of care in the pediatric ICU at OHSU is for patients admitted with an acute head injury to undergo routine QbMRI follow up to assess status of the injury rather than a repeat head CT. Our study team collected clinical data on these patients that included clinical interventions and then de-identified all head CT and QbMRI images for this cohort. The images were then independently reviewed by 2 neuroradiology fellows at OHSU (Please refer to **Figure 1**). The sensitivity of QbMRI to detect any radiographic injury was 85% (95% CI: 73, 93), but increased when evaluating clinically important TBIs to 100% (95% CI: 89, 100). The largest limitation of this study was the variable and often long time interval between acquisition of the head CT and QbMRI. The average length of time between the initial head CT and QbMRI was 27.5 hours with only 41% receiving both imaging tests within 12 hours of each other. Also, our preliminary data was collected by retrospective review. As such, it is very promising that our initial study had high sensitivity, but further prospective pilot data with a shorter interval between the index and reference test is needed to assess the discrepancy between the two types of lesions (radiographic vs clinically important) and feasibility of obtaining qbMRI in the setting of acute pediatric head trauma. While our study did not miss any clinically important TBIs, on further review of radiographic “missed lesions”, the study pediatric neurosurgeon noted signs of a healing bleed. This may suggest that they were “missed” because they were healed rather than present and not seen. All patients that did not have a lesion identified on QbMRI did not require significant clinical interventions and only underwent periods of observation in the hospital. However, this raises the need for a prospective trial to obtain QbMRI imaging within the same time frame sequentially after the initial head CT. The current proposed pilot study will provide further data to guide a larger, future multicenter study.

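### A hypothesis of no significant difference from CT cannot show comparable sensitivity, and 10 to 20 positives leave the exact lower limit at 69% to 83% even if QbMRI misses nothing

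*Combined protocol and SAP*

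**What the plan says.** The Hypothesis paragraph reads: "We hypothesize there is no significant difference of sensitivity and specificity of QbMRI for detection of clinically important traumatic brain injuries", with non-contrast head CT as the comparator. The Study Design overview describes the study as "comparing QbMRI (index test) to non-contrast head CT (reference test", so CT is also the standard against which QbMRI is scored.

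Number of Subjects fixes the size: "A total of 100 subjects will be enrolled in this pilot study". It then turns to whether that is enough: "To assess the adequacy of this proposed pilot sample, we calculated the number of positive head CTs obtained in our department". The site figure is "At OHSU 10% of CTs in patients less than 19 years of age were positive for an acute intracranial injury", and the conclusion is that the study should "have at least 10-20% with a positive acute TBI". No significance level, power, margin, minimum acceptable sensitivity or target interval width is given.

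Data Analysis plans sensitivity, specificity and predictive values with 95% confidence intervals. It names no test comparing QbMRI with CT; the only test named is for anxiolysis.

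Preliminary Data reports 85% (73, 93) sensitivity for any radiographic injury, which "increased when evaluating clinically important TBIs to 100% (95% CI: 89, 100").

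**The concern.** Three parts of the protocol do not meet. The hypothesis is framed so that a non-significant result would support it. The planned analysis is estimation. The sample is supported by a count of positives that is tied to neither.

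Sensitivity is the measure at stake, because a QbMRI false negative is a missed intracranial injury in a child. In a sample with few positives, a non-significant comparison is easy to obtain and says little. If it were read as equal accuracy, the pilot would hand the planned multicenter study a stronger conclusion than its data can carry.

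There is also a mismatch of target. The hypothesis concerns clinically important TBI, which the Background defines by surgery, hospital stay over 2 days, intubation or death. The 10% figure in Number of Subjects comes from diagnosis codes for any acute intracranial injury, including skull fracture. The number of positives that bear on the hypothesis is therefore not given and is probably below 10 to 20.

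**Working it through.** **Inputs.** From Number of Subjects: 100 children, a 10% positive rate at the site, and an expected share of at least 10-20%. From Preliminary Data: 100% (89, 100) and 85% (73, 93). Assumed here because the protocol is silent: exact (Clopper-Pearson) intervals and, for step 4 only, a two-sided 0.05 level.

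**1. The plan's own figure.** 100 × 0.10 = 10 reproduces the lower end. The upper end is 100 × 0.20 = 20, but the 20% cannot be derived, since neither the share of transfers nor their positive rate is stated. There is no power or precision figure to reproduce.

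**2. Precision with no misses.** When all n positives are detected, the exact 95% lower limit is 0.025^(1/n).
- n = 10: 0.025^(1/10) = 0.692, so 69% to 100%.
- n = 20: 0.025^(1/20) = 0.832, so 83% to 100%.

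**3. Precision with some misses.** 17 of 20 (85%) gives 62% to 97%, against 73% to 93% for any radiographic injury in the preliminary study. The no-miss limits of 69% and 83% compare with 89% for clinically important TBI there.

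**4. What a significance test would tolerate, if one were used.** Take CT-positive children with CT as the reference. CT is then positive in all of them, so the only discordant pairs are the b QbMRI misses. Two-sided p-values: exact McNemar 2 × 0.5^b; mid-p 0.5^b; uncorrected McNemar, chi-square = b on 1 df; continuity-corrected, chi-square = (b − 1)²/b on 1 df.

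| Misses b | Exact | Continuity-corrected | Mid-p | Uncorrected |
|---|---|---|---|---|
| 3 | 0.25 | 0.248 | 0.125 | 0.083 |
| 4 | 0.125 | 0.134 | 0.0625 | 0.046 |
| 5 | 0.0625 | 0.074 | 0.031 | 0.025 |
| 6 | 0.031 | 0.041 | 0.016 | 0.014 |

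The largest non-significant number of misses is 5, 5, 4 and 3 respectively. Three misses is an observed sensitivity of 70% with 10 positives or 85% with 20. Five misses is 50% or 75%.

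**5. Specificity.** With 10 to 20 positives there are 80 to 90 negatives. With no false positives the lower limit is 0.025^(1/80) = 0.955 or 0.025^(1/90) = 0.960, that is, about 95-96%. The weakness lies in sensitivity.

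**The case against.** The strongest reply is that this is a pilot meant to guide a larger study, and that its stated purpose is to remove the retrospective design and the average 27.5-hour gap between CT and QbMRI, not to gain precision. Number of Subjects sets out to assess adequacy but never declares the sample adequate or powered for the hypothesis. That stands: a wide interval is acceptable in a pilot, and no larger sample is asked for here. It does not rescue the hypothesis, which is still a claim about accuracy.

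A second reply is that Data Analysis already plans intervals, so 5 of 10 detected would be reported as 50% (19 to 81) and would visibly fall short. That also stands, and it confirms that the hypothesis has no analysis attached to it.

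A third is that 10-20% is presented as a floor. More positives would help, but with no misses a lower limit of 90% (an illustrative target) needs 36 positives, well above the stated range.

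Stronger readings are tempting, and the documents do not support them:
- A reader might infer that QbMRI could miss 5 of 10 or 5 of 20 lesions and the trial would report no difference. That depends on choosing an exact or continuity-corrected paired test at 0.05. The protocol names no test or level, and other two-sided variants tolerate only 3 or 4.
- A reader might extend step 4 to any definition of injury. It does not carry over to clinically important TBI as the Background defines it, because CT is not positive by construction when the condition is defined by clinical outcome.
- A reader might conclude that the hypothesis is almost bound to be confirmed. It also covers specificity: with 80 to 90 negatives and an assumed true specificity of 90%, an exact test would reject with probability 82% to 90%. At a true sensitivity of 75% with 20 positives it would reject 38% of the time.
- A reader might say the pilot has only a third or fewer of the preliminary study's positives. If that study's interval for clinically important TBI was exact, it implies 31 to 33 cases, and 20 is 61% to 65% of that.

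**Conclusion.** The point holds for sensitivity and should be fixed, though it does not stand in the way of running the pilot. A non-significant difference from CT cannot show comparable sensitivity, and the protocol plans no analysis that would. At the stated 10 to 20 positives, even a perfect result leaves sensitivities as low as 69% or 83% compatible with the data.

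Those limits rest on the protocol's expected count and on exact intervals, not on any choice of test. The range of 3 to 5 tolerated misses does rest on an assumed two-sided paired test at 0.05 and is illustrative. For clinically important TBI the precision is probably worse, by an amount the documents do not allow one to calculate.

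**What to change.** In Hypothesis, replace the no-significant-difference statement with an estimation aim: to estimate the sensitivity and specificity of QbMRI, with conclusions on sensitivity drawn from the exact (Clopper-Pearson) 95% lower limit. Add that a non-significant difference from CT will not be read as equal accuracy.

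In Number of Subjects, follow the expected count with the expected precision: with 10 to 20 positives the lower limit for sensitivity is about 69% to 83% even if none is missed. State that the pilot cannot establish sensitivity comparable to CT, and that the count refers to any acute TBI, with fewer clinically important cases likely.

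The cost is wording and a less favourable stated claim. No additional patients are needed. Reserving places for CT-positive children is not part of this fix, because it would distort the predictive values, which are among the primary outcomes.
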